7.1.3 Route of administration

Each dose of study vaccine will be administered via a single IM injection given in the deltoid muscle of the subjects' preferred arm. Aseptic technique will be used for the withdrawal and administration of each dose of study vaccine using a disposable sterile needle appropriate in length for each subject and a disposable sterile syringe.

7.1.4 Returns, reconciliation, and destruction

The investigator is responsible for keeping accurate records of the clinical supplies received from pharmaceutical supply or designee, the amount dispensed to and returned by the subjects and the amount remaining at the conclusion of the trial.

Sponsor/Investigator drug destruction is allowed provided the following minimal standards are met:

- On-site disposal practices must not expose humans to risks from the drug.
- On-site disposal practices and procedures are in agreement with applicable laws and regulations, including any special requirements for controlled or hazardous substances.
- Written procedures for on-site disposal are available and followed. The procedures must be filed with the Sponsor SOPs and a copy provided to pharmaceutical supporter upon request.
- Records are maintained that allow for traceability of each container, including the date disposed of, quantity disposed, and identification of the person disposing the containers. The method of disposal, ie, incinerator, licensed sanitary landfill, or licensed waste disposal vendor must be documented.
- Accountability and disposal records are complete, up-to-date, and available for pharmaceutical supporter to review throughout the clinical trial period as per the study agreement.

It is the Investigator's responsibility to arrange for disposal of all empty containers, provided that procedures for proper disposal have been established according to applicable federal, state, local, and institutional guidelines and procedures, and provided that appropriate records of disposal are kept.

Upon completion or termination of the study, all unused and/or partially used investigational product will be destroyed at the site per institutional policy. It is the Investigator's responsibility to arrange for disposal of all empty containers, provided that procedures for proper disposal have been established according to applicable federal, state, local and institutional guidelines and procedures, and provided that appropriate records of disposal are kept.

7.1.5 Expected adverse events / toxicities

Adult recipients of inactivated influenza virus vaccines may develop influenza-like reactions such as fever, feverishness (chills/shivering/sweating), gastrointestinal side effects (emesis and diarrhea), fatigue (tiredness), malaise (general unwell feeling), myalgia (body aches/muscular pain), arthralgia (joint pain), headache, and/or nausea. Some subjects may develop reactions at the injection site, including pruritus (itching), ecchymosis (bruising), erythema (redness), induration (hardness)/swelling, pain, and/or tenderness. With unadjuvanted licensed, inactivated influenza virus vaccines most of these reactions peak in intensity in the first 24 hours after vaccination and usually disappear without treatment within 1 or 2 days. Analgesics (e.g., acetaminophen, or ibuprofen or similar non-steroidal anti-inflammatory drugs (NSAIDs)) and rest may generally relieve or lessen these reactions. Bruising can sometimes occur due to the vaccination procedure.

In addition, post-marketing surveillance indicates the following adverse events of special interest (AESI) as potential risks for pandemic vaccines based on those identified for the seasonal influenza vaccines: neuritis, convulsions, severe allergic reactions, encephalitis, thrombocytopenia, vasculitis, and Guillain-Barré (GBS) syndrome. Reports of these reactions were rare; however, exact incidence rates cannot be precisely calculated.

Acute and potentially life-threatening allergic reactions are also possible. Very rarely, occurring in about 1 in 4 million people given a vaccination, there can be a serious allergic reaction to a vaccine. These reactions can manifest as skin rash (hives), swelling around the mouth, throat or eyes, difficulty breathing, a fast pulse, or loss of blood pressure. If these reactions occur, they can usually be stopped by the administration of emergency medications by the study personnel. As with any vaccine or medication, there is a very small chance of a fatal reaction (death), although researchers do not expect this to occur.

GBS: During the swine influenza (H1N1) vaccine campaign of 1976, some recipients developed a paralytic illness called Guillain-Barré syndrome (GBS). GBS is an acute inflammatory neuropathy characterized by weakness, hyporeflexia or areflexia, and elevated protein concentrations in cerebrospinal fluid. The rate of GBS was significantly increased in individuals receiving the 1976 swine influenza (H1N1) vaccine at about 1 per 100,000 vaccine recipients. This syndrome has not been seen consistently with other influenza vaccines. Most persons who develop GBS recover completely, although the recovery period may be as little as a few weeks or as long as a few years. About 30% of those with GBS still have residual weakness after 3 years and about 3% may suffer a relapse of muscle weakness and tingling sensations many years after the initial attack. Intensive surveillance of GBS after administration of inactivated influenza vaccines since 1976 has shown a slight

increase in risk over background cases (more than one additional case of GBS per million persons) following vaccination, typically with onset within 6 weeks after vaccination³⁶. Interestingly, although vaccination rates have increased in the last 10 years the numbers of reported cases of vaccine-associated GBS have declined³⁷. A recent study in Canada showed that the 2009 H1N1 vaccine was associated with a small but significant risk of GBS in persons 50 years and older³⁸. An active, population-based surveillance study conducted during the 2009-2010 influenza season found less than 1 excess GBS case per million doses of 2009 H1N1 vaccine administered – a rate similar to that associated with some previously administered annual influenza vaccines^{39,40}. Another study using the Medicare system showed an elevated risk of GBS with 2009 monovalent H1N1 vaccination (incidence rate ratio = 2.41, 95% confidence interval: 1.14, 5.11; attributable risk = 2.84 per million doses administered, 95% confidence interval: 0.21, 5.48)⁴¹. An international collaboration study also supported a conclusion of an association between 2009 H1N1 vaccination and GBS⁴².

8. CORRELATIVE/SPECIAL STUDIES

Assessment of biomarkers and changes relevant to influenza vaccination are paramount in this protocol.

Correlative Objective	IHC/Assay/Test	Tissue/Body Fluid Tested and Timing of Collection
Determine seroconversion and seroprotection	HAI titer	Peripheral blood at baseline, week 5, and week 21
B-cell and CD4 T-cell responses	Mass cytometry & other immunologic assays	Peripheral blood at baseline, week 5, and week 21.

8.1 Objective for lab 1 - Sanofi

8.1.1 Collection of specimens

Peripheral blood will be drawn at baseline, week 5, and week 21.

8.1.2 Specimen handling

Blood will be cryopreserved by the [name] laboratory and batch shipped to a central laboratory at Sanofi for processing.

8.1.3 Specimen analysis

HAI titer will be assessed.

8.1.4 Site performing study

Sanofi

8.2 Objective for lab 2 – [name] laboratory

8.2.1 Collection of specimens

30-40 mL of peripheral blood will be drawn, labeled and logged under the supervision of the principal investigator and in accordance with site specific SOPs.

8.2.2 Specimen handling

Specimens will be shipped to the [name] laboratory for processing – see protocol specific tissue collection worksheet.

8.2.3 Specimen analysis

- Mass cytometry: Phenotypic analysis of T and B cells, including plasmablasts and TFH cells will be performed by mass cytometry utilized a panel as described.⁴³
- Pneumococcal antibody responses by Elisa
- Antigen-specific T cells (CRM-197 and HA-specific T cells; T cells specific to control viral antigens (CMV, EBV).
- B cell receptor sequencing (selected cases)
- Single cell transcriptome analysis (selected cases).

8.2.4 Site performing study

[name] laboratory

9. RESPONSE

Time to progression (TTP): Time to progression is defined as the time from last treatment until progression. Patients who have died without evidence of progression are censored in the TTP analysis at the time of death and patients who are alive without progression are censored at the last disease assessment.

Progression-Free Survival (PFS): Defined as the time from last treatment to the disease progression or death from any cause. Patients who have not progressed or died are censored at the date last known progression-free. Patients with no on-study assessment will be censored at the time of registration.

Overall survival (OS): OS is defined as the time from randomization to death. Alive patients are censored at the date last known alive.

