3.4 Multiple myeloma

Multiple myeloma (MM) affects approximately 83,000 US citizens and over 50% of patients die within 5 years of diagnosis; more than half of patients older than 70 years with low albumin and high β 2microglobulin die within a year of diagnosis^{11,12}. Of the 30,330 new cases estimated in 2016 in the U.S.¹³, MM is twice as common in African Americans as Caucasians, and genetic changes accumulate as plasma cells degenerate from monoclonal gammopathy of undetermined significance, through smoldering myeloma, to MM¹⁴. MM is characterized by fractures, anemia, kidney failure, and hypercalcemia with a

predisposition for bacterial infections from the inherent immunoparesis and varicella reactivation often aided by proteasome inhibition¹⁵.

Advances in high-dose chemotherapy and stem cell transplantation have improved overall survival and event-free disease periods in patients with MM, but relapses are inevitable^{16,17}. New therapeutic agents, such as new generation proteasome inhibitors (carfilzomib and ixazomib), immunomodulatory agents (lenalidomide and pomalidomide, the histone deacetylase inhibitor (HDACi) panobinostat, and monoclonal antibodies (elutuzumab and daratumumab) have shown promising clinical benefit in patients with relapsed or refractory disease. Current treatments include regimens using proteasome inhibitors and/or immunomodulatory agents in combination with HDACi, alkylating agents, and monoclonal antibodies.

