4.2.4 Expected survival < 9 months

4.2.5 Prisoners

5. REGISTRATION, ACCRUAL, AND EARLY TERMINATION

5.1 Accrual

5.1.1 Enrollment overall

The research team member obtaining informed consent will tell the patient that (1) participation is voluntary, (2) participation or non-participation will not affect their usual care and management, and (3) patient confidentiality will be maintained if the results of the study are published. The potential toxicities of protocol therapy and the study calendar will be explained to the potential participant. Patients will be provided with a consent form to review, and an opportunity to discuss the study and have all questions answered.

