5.3 Duration of follow-up

Patients will be followed for 4 weeks after removal from study and patient records will be reviewed until death or 2 years from enrollment (whichever comes first) to assess progression and survival. Patients removed from study for unacceptable adverse event(s) will be followed until resolution or stabilization of the adverse event.

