10.4.6 Analysis of secondary endpoints

Time to event outcomes including TTP, PFS and OS will be assessed with patients censored at time of last follow-up. TTP, PFS and OS rates of two patient groups will be estimated with the Kaplan-Meier method and compared between different groups using the log-rank test, respectively. The TTP, PFS and OS of each patient group at specific time points, such as 1 year, 3 years, and 5 years, etc. will be estimated alone with 95% CI. Cox proportional hazards models will be used in the multivariable analyses to assess adjusted effects of biomarkers on the patients' TTP, PFS and OS after adjusting for other factors. The proportional hazards assumption will be evaluated graphically and analytically with regression diagnostics.

Protocol therapy related toxicities rate will be summarized using descriptive statistics such as frequencies and proportions. Differences in the proportion of patients who experience protocol-related toxicities will not be compared between cohorts.

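### Kaplan-Meier time-to-progression rates with deaths censored overstate, slightly, the proportion of patients who progress; cumulative incidence would fix this at almost no cost

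*Combined protocol and SAP*

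**What the plan says.** Section 9 measures TTP from last treatment to progression, and "Patients who have died without evidence of progression are censored in the TTP analysis at the time of death". In the same section PFS counts death from any cause as an event, and OS runs from randomization to death.

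Section 10.4.6 treats all three endpoints alike: "TTP, PFS and OS rates of two patient groups will be estimated with the Kaplan-Meier method", with a log-rank comparison. Estimates with 95% confidence intervals are planned "at specific time points, such as 1 year, 3 years, and 5 years". Cox models are planned for adjusted biomarker effects. Neither Section 9 nor Section 10 mentions cumulative incidence or competing risks.

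On follow-up, Section 5.3 says "patient records will be reviewed until death or 2 years from enrollment (whichever comes first) to assess progression and survival". TTP is analysed under secondary endpoints in 10.4.6 but is not among the objectives and endpoints of Sections 1 and 2.

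**The concern.** Death without progression is not ordinary censoring. Kaplan-Meier treats a censored patient as still able to progress, at the same rate as those remaining under observation. For a patient who has died this is false. One minus Kaplan-Meier then describes progression in a hypothetical population in which nobody dies first, and it exceeds the share of enrolled patients who actually progress.

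At stake are the absolute TTP rates by arm and their confidence intervals. There is also a trial-specific reason for care. The intervention is a vaccine, and the deaths it might plausibly affect are infectious deaths, which can occur without progression. If such deaths differed by arm or by biomarker group, the Kaplan-Meier TTP curves and the actual proportions progressing could compare differently between groups.

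**Working it through.** The plan states no TTP rate, so there is no figure of its own to reproduce. The size has to be explored under assumptions.

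**Inputs**
- Progression hazard p: 0.15, 0.30 and 0.50 per year. Assumed.
- Hazard of death without progression d: 0.02, 0.07 and 0.139 per year. Assumed. The top value converts the background figure in Section 3.4 ("over 50% of patients die within 5 years of diagnosis") to a constant hazard, −ln(0.5)/5 = 0.139, and treats every death as progression-free. About half of that is 0.07. The value 0.02 represents rare deaths.
- Patients per arm: 74 (Section 10.3).
- Horizon: 2 years (Section 5.3).

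**Formulas** (constant, independent hazards)
- One minus Kaplan-Meier estimates 1 − exp(−p·t).
- Cumulative incidence of progression is p/(p+d) × [1 − exp(−(p+d)·t)].
- Large-sample variance of the Kaplan-Meier estimate with complete follow-up to t: exp(−2p·t) × p/[n(p+d)] × [exp((p+d)·t) − 1].

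**Worked case**, p = 0.30, d = 0.07, t = 2:
- 1 − exp(−0.60) = 45.1%.
- 0.30/0.37 × [1 − exp(−0.74)] = 0.811 × 0.523 = 42.4%.
- Excess 2.7 points. The standard error is 6.0 points, so the excess is 0.45 standard errors.

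**Results at 2 years**

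| p | d | 1 − KM | Cumulative incidence | Excess (points) | Excess / SE |
|---|---|---|---|---|---|
| 0.15 | 0.02 | 25.9% | 25.4% | 0.5 | 0.1 |
| 0.15 | 0.07 | 25.9% | 24.3% | 1.6 | 0.3 |
| 0.15 | 0.139 | 25.9% | 22.8% | 3.1 | 0.6 |
| 0.30 | 0.02 | 45.1% | 44.3% | 0.8 | 0.1 |
| 0.30 | 0.07 | 45.1% | 42.4% | 2.7 | 0.45 |
| 0.30 | 0.139 | 45.1% | 39.9% | 5.2 | 0.8 |
| 0.50 | 0.02 | 63.2% | 62.2% | 1.0 | 0.2 |
| 0.50 | 0.07 | 63.2% | 59.7% | 3.5 | 0.6 |
| 0.50 | 0.139 | 63.2% | 56.4% | 6.8 | 1.1 |

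At 1 year, for d from 0.07 to 0.139, the same formulas give an excess of 0.5 points (p = 0.15, d = 0.07) to 2.4 points (p = 0.50, d = 0.139), at most 0.4 standard errors. With d = 0 the excess is zero. Incomplete follow-up would enlarge the standard errors and shrink the ratios.

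**Cross-check by probabilities.** Fix one minus Kaplan-Meier at 20% at 2 years. If the net 2-year probability of death without progression is 2%, 5%, 10% or 24%, the cumulative incidence is 19.8%, 19.5%, 19.0% or 17.6%. The 24% is 1 − exp(−2 × 0.139). A simulation of 400,000 patients for that last case also gave 17.6%.

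**The case against.** **Censoring at death is legitimate for a cause-specific analysis.** This stands. The log-rank test and Cox model on TTP compare cause-specific hazards and need exactly this censoring, so Section 9's wording should not be removed. Only the absolute rates are in question.

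**The plan never says it will report one minus Kaplan-Meier as the proportion progressing.** True: 10.4.6 speaks only of rates. But rates at named years with confidence intervals will naturally be read that way, and the ambiguity is worth settling. PFS and OS, reported alongside, limit the damage.

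**The protocol does not predict high mortality in this trial.** This also stands. A reader might infer from Section 3.4 that substantial mortality is expected. That sentence is background on myeloma, counted from diagnosis and covering all deaths. The trial admits any plasma cell dyscrasia (4.1.1), and Section 3.5 describes a spectrum starting at low-risk MGUS. Section 4.2.4 excludes "Expected survival < 9 months". Only death before progression causes the bias, and Section 3.4 also says of myeloma that "relapses are inevitable", so many deaths would follow progression.

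**Large gaps at 3 and 5 years cannot arise.** A reader might apply the formulas at the later times named in 10.4.6 and obtain much larger excesses. Record review ends 2 years from enrollment, so those estimates lie beyond the data. That mismatch between 5.3 and 10.4.6 is a separate matter that a change of estimator does not cure. TTP follow-up may be shorter still. If last treatment means the last study vaccine, the week-17 dose leaves (104 − 16)/52 = 1.7 years in the experimental arm, where the case p = 0.30, d = 0.07 gives an excess of 2.1 points.

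**Conclusion.** The point holds in a limited form. The pairing of censoring at death with Kaplan-Meier rates is in the text, and the direction of the bias is certain if any patient dies without progression. Its size is not known from the documents. Under the assumed hazards it is 1.6 to 6.8 points at 2 years, about one standard error or less, and close to nothing if such deaths are rare. This rests on constant, independent hazards and complete follow-up of 74 patients per arm.

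A reader might go further and conclude that the TTP comparison between arms is invalid or that the trial's result is at risk. The documents do not support that. The TTP tests remain valid as cause-specific comparisons, PFS and OS handle death properly, TTP is not a stated objective, and week-21 seroprotection does not depend on it. Nor do the documents show that deaths without progression will differ by arm; that is only a possibility to guard against. This is a minor improvement, worth making because it is cheap.

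**What to change.** In 10.4.6, report the absolute TTP rates as cumulative incidence of progression (Aalen-Johansen estimator with its 95% confidence interval), with death without progression as a competing event. Show the cumulative incidence of death without progression beside it, by arm. Choose times within the 2-year follow-up.

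In Section 9, keep the censoring at death, but state that it applies to the log-rank and Cox analyses of TTP, which are cause-specific, and that for cumulative incidence death without progression is a competing event. Keep Kaplan-Meier for PFS and OS.

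The cost is a few sentences and an estimator found in standard survival software. No new data are needed, because records are already reviewed for progression and survival. The one drawback is that the TTP figures become less directly comparable with published Kaplan-Meier TTP curves.

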3.5 Myeloma patients and influenza

In myeloma patients on treatment, there is a 20% likelihood of influenza-like illness^{18,19} with a 10-fold higher risk of viral URIs²⁰ than the general population. Even patients with precancerous conditions such as monoclonal gammopathy of undetermined significance (MGUS) and Smoldering Myeloma are at increased risk of bacterial and viral infections²¹. While only 3-5% of these viral illnesses are influenza, the mortality is high in the immunosuppressed and post-influenza bacterial pneumonias have high morality. In addition myeloma and it's precursor diseases provide a novel window to studying vaccination in a full spectrum of immunosuppression from non-cancerous low-risk MGUS to end-stage lymphopenic patients with relapsed multiple myeloma.

Vaccine preventable illnesses have not been prevented in patients with myeloma due in part to lack of seroresponse with standard dosing algorithms. Based on available trial data restricted to myeloma patients, serologic protection (HAI titer ≥ 40) to all three influenza strains following trivalent influenza vaccine is achieved in less than 20% of myeloma patients in each trial²²⁻²⁴. There have been two trials investigating the benefit of booster vaccine in myeloma patients. In 2005 Ljungmen et al, studied 70 patients with hematologic malignancies (10 with myeloma and 4 with WM) and administered a booster dose 30 days following standard influenza vaccine booster and found no increase in serologic protection²⁵. More recently, in the past 2013-2014 flu season, Hahn et al gave a standard dose influenza booster vaccine after 30 days to 25 myeloma patients and noted a doubling of serologic protection (HAI titer ≥ 40) from 14% to 33%²⁶. This suggests that there may be a role for booster vaccines in patients with hematologic malignancies, however there is obviously much room to improve.

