5.2 Duration of therapy

Patient may remain on study until one of the following criteria applies:

- Intercurrent illness that prevents administration of vaccine or follow-up,
- Per physician discretion in the setting of unacceptable adverse event(s), or other medical condition or situation occurs such that continued participation in the study would not be in the best interest of the participant. In patients who are randomized to the experimental arm only, specific adverse events include grade 3 adverse event that occurs without alternative etiology in the 7 days following the first study vaccination

- Patient decides to withdraw from the study, or
- General or specific changes in the patient's condition render the patient unacceptable for further treatment in the judgment of the PI.
- Termination or suspension of the study for safety reasons

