6. STUDY PROCEDURES & SCHEDULE

6.1 Agent administration

Treatment will be administered on an outpatient basis. Reported adverse events and potential risks of protocol therapy are described in the pharmaceutical section.

No investigational or commercial agents or therapies other than those described in this protocol may be administered with the intent to vaccinate the patient for influenza or *S. pneumoniae*.

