10.2 Analysis datasets

Safety Population: The safety analysis dataset will include all eligible patients who begin treatment and receive at least one dose of protocol therapy. Patients will be analyzed in the cohort to which they were enrolled.

Efficacy Evaluable Population: All evaluable patients will be included in the analysis of efficacy endpoint. The term evaluable is defined as any eligible patient who receives at least one dose of protocol therapy and does not withdraw consent until the patient's first response assessment. Patients who fail to have a response assessment due to early progression or death will be categorized as non-responders.

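### PFS and TTP are timed from an undefined last treatment, which on the vaccine reading falls up to 16 weeks later in the three-dose arm, and the 3- and 5-year rates lie beyond the 2-year record review

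*Combined protocol and SAP*

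**What the plan says.** Section 9 sets two different origins. For TTP, "Time to progression is defined as the time from last treatment until progression"; PFS is "Defined as the time from last treatment to the disease progression or death from any cause". For OS, "OS is defined as the time from randomization to death". Section 9 adds, for PFS: "Patients with no on-study assessment will be censored at the time of registration".

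*Last treatment* is not defined there or elsewhere. Most operational text uses the word for the study vaccine:

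- Section 6.1: "Treatment will be administered on an outpatient basis".
- Section 10.2, safety population: "all eligible patients who begin treatment and receive at least one dose of protocol therapy".
- Section 5.2, among the reasons to come off study, changes in condition that "render the patient unacceptable for further treatment in the judgment of the PI".

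The background uses it for anti-myeloma therapy. Section 3.5: "In myeloma patients on treatment, there is a 20% likelihood of influenza-like illness".

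Under Sections 6.1.1, 6.1.2 and 6.5, controls receive Fluzone HD once, at week 1, and the experimental arm receives it at weeks 1, 9 and 17. The Schema adds PCV13 at week 5 in both arms, unless the patient has already had a pneumococcal vaccine that calendar year.

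Section 10.4.6, under secondary endpoints, plans Kaplan-Meier curves and log-rank tests of TTP, PFS and OS between the two groups, and gives 1, 3 and 5 years as examples of times at which rates will be estimated. Section 5.3 ends the record review for progression and survival at death or 2 years from enrollment.

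**The concern.** A randomized comparison of time-to-event outcomes needs an origin that does not depend on the arm or on what happens after randomization. Timing from the last vaccine dose breaks both conditions: the origin is later by design in the three-dose arm, and within that arm it depends on how many doses the patient went on to receive. A difference in PFS or TTP could then come from the clock alone. If *last treatment* means anti-myeloma therapy, patients share no common origin, and untreated patients (Section 3.5 describes a spectrum that starts at low-risk MGUS) have none.

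Two further problems follow on the vaccine reading. A patient who progresses between doses and is still vaccinated would have a negative time; Section 5.2 does not list progression as a reason to stop, although the PI may stop for a change in condition, and no rule covers the case. Censoring at registration puts the censoring date at or before the origin.

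Separately, the 3- and 5-year rates cannot be estimated from a 2-year review. For OS this is so whatever *last treatment* means.

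PFS is also the outcome of the peak-HAI analysis in Section 10.4.5, so the undefined clock reaches a second planned analysis.

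**Working it through.** The plan gives no event count, power or rate for TTP, PFS or OS, so there is no figure of its own to reproduce. The check has three parts.

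**1. Calendar arithmetic (Sections 5.3, 6.5, Schema).**

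- Difference in origin: week 17 − week 1 = 16 weeks = 112 days (107 to 117 with the 5-day visit window). It is 8 weeks if dosing ends at week 9.
- If PCV13 counts as treatment: week 17 − week 5 = 12 weeks, against controls who receive it.
- Maximum follow-up after dose 3: 104 − 16 = 88 weeks. For those patients even a 2-year PFS or TTP is out of reach on the last-dose clock.
- Measured from enrollment, the 3- and 5-year points lie 12 and 36 months past the end of review.

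**2. Expected distortion with no true effect.** Assumptions: constant hazard λ, the same in both arms; S(t) = exp(−λt); doses at 0, 8 and 16 weeks after enrollment; all event-free patients dosed on schedule; review to week 104; clock at the last Fluzone HD dose before the event. Events are then the same in both arms, but the experimental arm loses person-time:

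- Control person-time per patient: PT = (1 − S(104))/λ
- Lost in the experimental arm: 8·S(8) + 8·S(16)
- Rate ratio = PT / (PT − 8·S(8) − 8·S(16))

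Worked for a 24-month median (104.36 weeks): λ = 0.693147/104.36 = 0.006642 per week; S(8) = 0.9483, S(16) = 0.8992, S(104) = 0.5012. PT = 0.4988/0.006642 = 75.10 weeks. Loss = 7.59 + 7.19 = 14.78. Ratio = 75.10/60.32 = 1.245.

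**3. Simulated log-rank test** (two-sided 0.05, 74 per arm; 40,000 trials per median on the last-dose clock, 10,000 in the other settings). The HR is experimental over control, so values above 1 count against three doses.

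| Assumed median PFS (months) | 12 | 24 | 36 | 60 | 120 |
|---|---|---|---|---|---|
| Rate ratio, closed form | 1.32 | 1.245 | 1.22 | 1.21 | 1.19 |
| Cox HR, simulated | 1.31 | 1.24 | 1.22 | 1.21 | 1.20 |
| Type I error, last-dose clock | 28% | 15% | 11% | 8% | 6% |
| Type I error, from randomization | 5% | 5% | 5% | 5% | 5% |
| Last-dose clock, PCV13 counted, half receive it | 22% | 12% | 10% | 8% | 6% |
| Last-dose clock, PCV13 counted, all receive it | 18% | 10% | 9% | 7% | 6% |
| Experimental events before week 17 excluded | 5% | 5% | 5% | 5% | 5% |

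The last row gives HR 1.00, so the bias depends on a handling rule that the plan does not state. On the last-dose clock, apparent 1-year PFS at medians of 12, 24 and 36 months is 40%, 64% and 74% with three doses against 50%, 71% and 79% in controls, again with no true effect.

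Precision from randomization: expected events = 148·(1 − S(104)) = 111, 74, 55, 36 and 19. The HR detectable at 80% power is exp(2·(1.96 + 0.8416)/√events) = 1.70, 1.92, 2.13, 2.55 and 3.60.

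**The case against.** The strongest reply concerns weight. PFS, TTP and OS appear in no objective in Sections 1 and 2 and not in the sample size; no decision rule uses them, and the comparisons are unpowered. That is correct and limits the reach of the point. Section 10.4.6 nevertheless plans them as formal between-arm tests, and they should be interpretable if they are reported.

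The type I figures rest on stacked assumptions: the vaccine reading, a clock at the last dose before the event, an assumed median, full dosing and complete follow-up. This also stands. If 90% receive dose 2 and 80% of those receive dose 3, the error falls to about 20%, 11%, 8 to 9%, 7% and 6% across the five medians; at 80% and 60% it is about 15%, 9%, 7%, 7% and 5%. Nothing in the documents supports a 12-month median for the whole population, so the 28% is the top of a range and not an estimate.

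The vaccine reading is the more natural one. Section 11.7 also speaks of study drug treatment, and the anti-myeloma reading rests on a background sentence. That strengthens the main point, because the vaccine reading is the one that ties the origin to the arm.

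How often the registration-censoring rule would apply is unknown. The modified myeloma assessment is optional, and Section 10.3 reports 27 of 50 first-season patients missing week 21, but a missed week-21 visit does not mean no assessment at all when progression comes from record review. The conflict between the rule and the origin remains.

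The 3- and 5-year points are only examples, and the 1-year rate can be estimated. True, but two of the three examples cannot be delivered.

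**Conclusion.** The concern holds. As written, PFS and TTP have an undefined origin that differs from the origin of OS. On the reading that the operational text favours, it differs between arms by up to 16 weeks and depends on doses given after randomization. The resulting error is not fixed by the documents: under a constant hazard it runs from none (early experimental-arm events excluded) to an apparent HR of about 1.2 to 1.3 against three doses, with type I error of 6% to 28% over assumed medians of 120 down to 12 months and full dosing. The 3- and 5-year rates cannot be produced from the planned 2-year review. This should be corrected before these endpoints are analysed. It does not touch the week-21 seroprotection endpoint or its sample size.

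**What to change.** In Section 9, count PFS and TTP from randomization in both arms, as OS already is, and drop *last treatment* from both definitions. Censor patients with no on-study assessment at randomization (day 1). On this clock the difference in origin falls from 112 days to 0, no event after randomization has a negative time, and follow-up runs to 24 months in both arms.

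In Section 10.4.6, replace the 3- and 5-year rates with time points inside the review, for example 1 year, and 2 years with numbers at risk shown. If later rates are wanted, extend the record review in Section 5.3 instead.

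The cost is wording in Sections 9 and 10.4.6, with no new data. Only keeping the later time points would cost more: 12 or 36 further months of chart review for the 3- and 5-year rates.
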